## **Stage 2, Establish Sensory Tolerance in Expected Satiety of a fat reduced snack model.**

**Note: the methodology proposed here is based on the stage 2 of the pilot study (SCFP 14\_17), except that it is testing a fat reduced snack model.**

Reduced fat products are typically reformulated to match the perceived texture and mouthfeel of the original product. Changing fat droplet size in emulsions can alter both expected and actual satiety. This stage aims to quantify sensory tolerance to fat reduction by using emulsion technology developed at the Quadram Institute, Norwich. In this study emulsions will be applied to an expanded snack product (extruded corn snack) in a similar manner to the coating of a commercial product where oil is normally applied to yield a fat content of approximately 32% (w/w) on the final product. As in the pilot study, an emulsification process will be used to incorporate water or gel droplets into the oil phase to reduce the fat content of the product whilst aiming to mimic the physical properties of the oil normally applied. The type of droplets (e.g. Gel in Oil versus Water in Oil droplets) and the proportion of droplets will be varied to create a range of emulsion models of varying reduced fat content. Direct addition of free fatty acid (oleic acid) at levels slightly above the threshold level of the hypertasters will also be included in one of the reduced fat emulsion models.

These snack products will be supplied by Pepsico. Findings will be generic and will also apply to other systems.

**Aim:** To define sensory tolerance; the maximum amount fat can be lowered by without leading to significant changes in expected satiety, fatty perception and/or consumer liking using standardized measures. Learnings from the pilot emulsion study will be used to estimate the maximum fat reduction, so only a limited number of fat levels will be trialled in the snack system, but the influence of free fatty acids and emulsion type can also be tested for effects on perception and expected satiety within the snack model.

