### **Method:**

1. The emulsion snack models (maximum of 6 small snack samples) will be presented to subjects in a monadic sequential manner (i.e. one at a time) in a balanced order. After tasting each sample, participants will rate a variety of measures including: hedonic liking, fat perception ("how fatty do you think this product is"), mouthfeel perception (e.g. mouthcoating). Questions that are not relevant to the study hypothesis will also be asked to try to

prevent biasing the participants through focusing them on fat perception (e.g. "how salty" "how strong is the flavour"). Following tasting of each sample, they will also be shown an image of a full portion of the sample (approximately 40 g) and asked to rate expected satiety (e.g. "If you were to consume a full portion of this product (show picture), how full do you think you would feel?" "How long do you think it would be before you felt hungry again?"). Unstructured line scales (visual analogue scales, VAS) will be used, participants will receive training in scale use (see example in Appendix G).

2. For three of the samples, the high fat control, low fat control, and maximum-reduced fat emulsion product, we will examine breakdown of the product in the oral cavity by asking the volunteers to provide expectorated boluses. In each case they will be asked to chew a set amount of snack (e.g. 10 g) for a set amount of time (e.g. 20 s) and then to spit out the sample.

**Output:** These tests will determine the maximum level to which fat can be reduced in snacks without causing a significant difference in expected satiety, fatty perception or liking. This will determine whether the emulsion type and / or the addition of a low level of free fatty acids influences expected satiety, fatty perception or liking. The expectorated boluses will be used to determine the fat distribution and snack breakdown characteristics between the high fat control and reduced fat emulsions as these characteristics may help to explain differences in perception,

**Stage 3, Establish Mouth Gut Discordance of a fat reduced snack model (quantified as the discrepancy between expected satiety from sensory signals and measured satiety through a preload consumption study).**

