**Method:**

1. Using a standard preload study design, and the same fat-emulsion snack model from stage 2, we will contrast effects of 3 test samples in a balanced cross-over design. The 3 samples are: (i) Positive control with 100% of the applied spray being oil (approximately 13g fat per 40 g snack portion); (ii) Low fat snack model, where the same amount of spray is applied to the snack fat but as the reduced fat emulsion determined in stage 2, and (iii) Negative control with the same % fat reduction as in sample (ii) achieved through lowering the amount of oil sprayed onto the snack base.

As it is a 3-way cross over design, participants need to attend 3 visits. Pre-menopausal women differ in hunger at different stages of the menstrual cycle and will be asked to avoid the week prior to their menstrual cycle.

Menstruating women have two phases: follicular and luteal with ovulation occurring at the end of the follicular phase. A number of studies have reported that women in the luteal phase (low estrogen and high progesterone) have higher caloric intake and consume more carbohydrates than women in the follicular phase (high estrogen but low progesterone); hence we aim to avoid the luteal phase.

2. Participants will attend the Food and Nutritional Sciences(FNS) sensory science centre following an overnight fast (approximately 08:50, volunteers staggered by a few minutes) and given a standard study breakfast of cereal, milk and orange juice. They will be asked to clean their teeth and use a mouthwash (provided by the study team) between 7 and 8 am; this is to standardise mouth care procedures as oral microflora can contribute to oral lipase activity and the breakdown of dietary fats. They will be given the test snack (pre-load study food, approximately 50 g) to consume at +2 hours (approx. 11 am) on each study day. We anticipate that the low-fat snack model with matched sensory expected satiety will have a fat reduction of over 25 % but that this may reach a 60% reduction.

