3. Primary outcomes: Hunger and satiety will be measured (by VAS, see example in Appendix H) before breakfast, between breakfast and the pre-load study food, immediately after consumption, and every 30 minutes up to 1 hours post pre-load (approx. 12:00). Three hours after breakfast and 1h post the preload study food participants will be given an ad-libitum pasta meal. An excessive portion size will be given to each participant and they will be asked to eat until full. This is achieved by providing a 500 g portion on one plate and replacing it after 5 minutes

with a second 500g portion plate. Weight of pasta consumed will be measured.

4. Secondary outcomes; Circulating biomarkers of satiety and hunger: Participants will be asked to consent to provide biofluid samples for the determination of biomarkers of satiety and hunger. The study is powered for the preload study differences in ad-libitum intake and not on the circulating biomarkers; therefore, if volunteers expressed a preference to not provide blood samples they will not be excluded from the study, but continue with the behavioural study only. The circulating biomarker data we obtain will help to explain mechanisms behind the study behavioural outcomes and provide data on which future studies can be powered. The following samples will be taken after informed consent (appendix C) is given:

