**Appendix G: Examples of Line Scales Participants will Use for Rating in Stage 2**

How much did you like this sample?	Dislike Extremely		Like Extremely
How sour was the sample?	Not Sour		Very Sour
How salty was the sample?	Not Salty		Very Salty
How fatty was the sample?	Not Fatty		Very Fatty
How thick was the sample?	Very Thin		Very Thick
How mouthcoating was the sample?	Not mouthcoating		Very Mouthcoating
If you were to eat a full potion of the sample (show picture):			
How full do you think you would feel?	Not Full		Very Full
How long would it be before you felt hungry?	A short time (< 30 minutes)		Along time (> 2 hours)

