**Appendix H: Examples of Line Scales Participants will Use in Stage 3**

How hungry do you feel?	Not Hungry at all		Extremely Hungry
How strong is your desire to eat?	Not at all		Extremely
How full (satiated) do you feel?	Not Full at all		Very Full
How much do you think you could (or would want to) eat right now?	Nothing at All		A Very Large Amount

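### The Stage 3 preload is about 50 g, but the control is described per 40 g portion and expected satiety is rated on a picture of about 40 g

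*Protocol*

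**What the plan says.** All of the following is current text in the Protocol.

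- **Portion eaten** (Section 2.2, Stage 3 Method, item 2): "They will be given the test snack (pre-load study food, approximately 50 g) to consume at +2 hours".
- **Portion used to describe the control** (Section 2.2, Stage 3 Method, item 1): the positive control is given as "approximately 13g fat per 40 g snack portion".
- **Portion rated** (Section 2.2, Stage 2 Method, item 1): after tasting each sample, "they will also be shown an image of a full portion of the sample (approximately 40 g) and asked to rate expected satiety".
- **Fat content** (Section 2.2, Stage 2 introduction): the comparison is with a commercial product "where oil is normally applied to yield a fat content of approximately 32% (w/w) on the final product".
- **What Stage 3 is meant to measure** (Section 2.2, Stage 3 heading): mouth-gut discordance, "quantified as the discrepancy between expected satiety from sensory signals and measured satiety through a preload consumption study".
- **What the study is powered on** (Section 2.2, Stage 3 Method, item 4): "The study is powered for the preload study differences in ad-libitum intake and not on the circulating biomarkers".

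Section 3.1 (Sample Size) brings in a third mass. It likens the energy of a 35 g snack at 32% fat to the 836 kJ safflower-oil preload of a cited study. Stage 3 item 1 says that Stage 3 uses the same snack model as Stage 2, so a change of product does not explain the difference.

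**The concern.** The mass of the preload is the dose of the intervention, and the Protocol fixes it in two ways. A person following item 2 would serve 50 g. A person preparing the control from item 1 would take the portion to be 40 g with 13 g of fat.

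The scientific consequence lies in the discordance measure. One side of it is the satiety that participants expect from a pictured 40 g. The other is the satiety they report after eating 50 g. The example scales make a direct comparison possible on fullness: Appendix G asks "How full do you think you would feel" and Appendix H asks "How full (satiated) do you feel". A difference between those two scores would then include the effect of 25% more food, which has nothing to do with mismatched mouth and gut signals.

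**Working it through.** **Inputs from the Protocol.** Served mass 50 g; pictured mass 40 g; control 13 g fat per 40 g; fat content about 32%; anticipated fat reduction from 25% to 60% (Stage 3 item 2); reference preload 836 kJ, likened to 35 g of snack (Section 3.1).

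**Step 1. Reproduce the stated fat figure.** Fat = fat fraction × mass.
- At 40 g: 0.32 × 40 = 12.8 g, which rounds to the stated 13 g. In reverse, 13 / 40 = 32.5%.
- At 50 g: 0.32 × 50 = 16.0 g.

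The 13 g figure therefore belongs to a 40 g portion.

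**Step 2. Eaten against rated mass.** 50 / 40 = 1.25, so the portion eaten is 25% larger.

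**Step 3. Fat removed from the reduced-fat samples**, at reductions of 25% and 60%.
- At 40 g: 0.25 × 12.8 = 3.2 g to 0.60 × 12.8 = 7.7 g.
- At 50 g: 0.25 × 16.0 = 4.0 g to 0.60 × 16.0 = 9.6 g.

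**Step 4. Energy against the 836 kJ reference in Section 3.1.** Two bases are shown, because the Protocol does not state the energy content of the snack.

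*(a) Treating the Protocol's 35 g equivalence as exact:* 836 / 35 = 23.9 kJ/g. Then 40 g gives 955 kJ (40 / 35 = 1.14, +14%) and 50 g gives 1194 kJ (50 / 35 = 1.43, +43%).

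*(b) With assumed energy factors that are not in the Protocol:* fat 37 kJ/g, remainder 14 to 17 kJ/g.

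| Mass | Fat part | Remainder | Total | Against 836 kJ |
|---|---|---|---|---|
| 35 g | 11.2 × 37 = 414 | 23.8 × (14 to 17) = 333 to 405 | 748 to 819 kJ | −11% to −2% |
| 40 g | 12.8 × 37 = 474 | 27.2 × (14 to 17) = 381 to 462 | 854 to 936 kJ | +2% to +12% |
| 50 g | 16.0 × 37 = 592 | 34.0 × (14 to 17) = 476 to 578 | 1068 to 1170 kJ | +28% to +40% |

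On either basis 40 g stays nearer the reference preload than 50 g.

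**Step 5. Which comparisons are affected.** Item 2 gives the same mass on each study day, so all three samples are eaten at one mass. Contrasts between samples within Stage 3 therefore do not carry the discrepancy, and neither do contrasts between samples within Stage 2, where all pictures show about 40 g. Only a comparison across the two stages does.

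**The case against.** The strongest reply has four parts.

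1. *The fat figure may be a composition ratio.* Read as 32.5% fat, 13 g per 40 g is compatible with serving 50 g. This reading is open, although the Protocol calls the 40 g a snack portion and Stage 2 calls about 40 g a full portion. If it is granted, the conflict between the picture and the preload remains.

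2. *Discordance may be judged between products.* The text before the Stage 3 Method speaks of rebound hunger and over-eating after fat reduction, which is a contrast between samples. A common mass would cancel there, apart from any interaction with product. This part stands, and it limits the harm to a direct comparison of expected with measured satiety. The Stage 3 heading describes discordance in those terms, but no analysis by subtraction is prescribed.

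3. *A direct comparison would be hard to read even with equal masses.* Appendix G asks about a hypothetical portion after a small taste. Appendix H asks about current fullness, and on the study day the snack follows a breakfast by two hours. The low anchors also differ, and both appendices only give examples. This stands too, but it is no reason to add an avoidable difference in portion size.

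4. *Both masses are approximate.* A 25% gap between two nominal values in one method section is more than that word can reasonably cover.

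The energy figures are side evidence. They rest on a loose statement of similarity or on assumed factors, and they do not show which mass was intended.

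**Conclusion.** The inconsistency is real and is not resolved anywhere in the Protocol. As written, the portion eaten is 25% larger than the portion rated, and the control portion would hold about 16 g of fat where about 13 g is stated. These figures need only the Protocol's own masses and its 32% fat content.

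The consequence is limited. The appetite and intake contrasts between samples, including the intake outcome on which the study is powered, are not biased by it. A direct comparison of expected with measured satiety would mix in a portion-size difference. Its effect on the ratings is unknown, because the Protocol gives no relation between grams and fullness. This is a minor point, held with high confidence.

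**What to change.** State one portion mass and use it throughout.

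- **Preferred:** change 50 g to 40 g in Stage 3 Method item 2. This agrees with the Stage 2 picture and with the 13 g fat figure, and it stays nearer the 836 kJ reference. The sponsor should confirm that 40 g is what was meant.
- **If 50 g is intended:** show a 50 g portion in the Stage 2 picture and describe the positive control as about 16 g of fat per 50 g portion.

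Under either choice, recheck the Section 3.1 comparison against the chosen mass and restate it if it no longer holds. Replacing the 35 g by the new number is not enough, because the energy changes with it.

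The cost is one number in one sentence for 40 g, or a new picture and a changed fat figure for 50 g, plus the check of Section 3.1 in both cases. No extra participants or visits are needed.

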## 2.3

Where will the project take place? Sensory Science Centre and Hugh Sinclair Unit of Human Nutrition and The Chemical Analysis Facility NMR Laboratory

If the project is to take place in Hugh Sinclair Unit of Human Nutrition, projects must be reviewed and approved by the Hugh Sinclair Manager ([name] [[contact]](mailto:[contact])

Signed..... (Hugh Sinclair Unit Manager) Date:.....

2.4

**Funding**

Is the research supported by funding from a research council or other *external* sources (e.g. charities, business)? Yes/ (please delete)

**If Yes, please give details:** BBSRC, Unilever and Pepsico.

Please note that *all* projects (except those considered as low risk, which would be the decision of the School's internal review committee and require Head of Department approval) require approval from the University Research Ethics Committee.

2.5

**Ethical Issues**

Could this research lead to any risk of harm or distress to the researcher, participant or immediate others? Please explain why this is necessary and how any risk will be managed.

All samples used in the study that have been produced at Pepsico will be manufactured under the Good Manufacturing Guidelines and will have undergone microbiological clearance testing. The levels of fat and saturated fat we are giving to participants is not excessive, however we will screen out participants with hypercholesterolaemia (high cholesterol) determined at screening, known to have cardio-vascular problems, or that are on a low fat diet (see Appendix C).

Venepuncture and cannulation may cause a small bruise at the site of needle penetration; it will be performed by the research nurses. Clinical cover (research nurse) will be available at all times during the 4 h study visits. However, in case of an emergency (e.g. fainting, blood spillage) researchers will take immediate action according to the Department of Food & Nutritional Sciences relevant SOP that describes in detail the actions that need to be taken by the researchers. Also, a Departmental First Aider will be available in the building when blood samples are taken both at screening and during the study visits. In case of emergency, the research staff will call the emergency services (999).

*(this box may be expanded as required)*

2.6

**Deception**

Will the research involve any element of intentional deception at any stage (i.e. providing false or misleading information about the study, or omitting information)?

[If so, this should be justified. You should also consider including debriefing materials for participants, which outline the nature and the justification of the deception used]

Yes: the study will inform the participants that we are interested in their appetite, liking and perception, however we cannot tell them that we are specifically interested in fatty perception alone because this will bias their responses. Therefore, we will ask questions relating to their perception of attributes other than fat

in Stage 2. In Stage 3 we will not draw attention to the snack (mid-morning) component of the visit (i.e. the pre-load samples), although participants may realise that it is this component we are investigating as they will have scored expected satiety of this component in Stage 2.

2.7

**Payment**

Will you be paying your participants for their involvement in the study? Yes/No (delete)

If yes, please specify and justify the amount paid

Participants will be reimbursed for their time as follows:

Stage 1 (screening and subject characterisation): participants will be reimbursed £10 for the one visit (approximately 1 h).

Stage 2: participants will be reimbursed £10 for the one visit (approximately 1 h).

Stage 3: participants will be reimbursed £60 for the three visits (three half days) if they are not providing blood, urine and saliva samples; however, they will be reimbursed to total of £140 for the three visits if they are also providing blood, urine and saliva samples.

Note: excessive payment may be considered coercive and therefore unethical. Travel expenses need not to be declared.

2.8

**Data protection and confidentiality**

What steps will be taken to ensure participant confidentiality? How will the data be stored?

Volunteers will be given a participant number, and throughout data collecting will be referred to by this number. Data linking the name of the participant to their participant number will be kept in a locked filing cabinet in a locked office in the Department of Food and Nutritional Sciences. The Department of Food & Nutritional Sciences, where the study will be performed, is fully licensed under the Human Tissue Act 2004 and as such will adhere to the guidelines necessary for the storage of saliva and blood samples.

2.9

**Consent**

Please describe the process by which participants will be informed about the nature of the study and the process by which you will obtain consent

Participants will be given a consent and screening form (appendix C) as well as the participant information sheet which will be explained to the volunteers in order that they have the opportunity to ask any questions. These questions will be suitably addressed before they are asked to sign the consent form. No testing will commence before a consent form is signed.

Participants that have already consented to the pilot study, and signed to say they can be contacted again, will be contacted directly about this main study, however they will be asked to sign the consent form for this subsequent main study in addition to their pilot study consent form.

2.10

**Genotyping**

Are you intending to genotype the participants? Which genotypes will be determined?

Yes. Genes related to sensory perception will include, but are not limited to, *CD36*, *CA6* and *TAS2R38*. Key target genes related to food intake via either gut hormone release or reward will also be genotyped (key genes here will include, but are not limited to, *FTO*, *CNR1* and *DAT1*). (See Gene fact sheet as part of the Participant Information Sheet, Appendix E). Only genes related to sensory perception, gut hormone release and food reward mechanisms will be investigated.

Please note that a copy of all information sheets on the implications of determining the specific genotype(s) to be undertaken must be appended to this application.

**SECTION 3: PARTICIPANT DETAILS**

3.1

**Sample Size**

How many participants do you plan to recruit? Please provide a suitable power calculation demonstrating how the sample size has been arrived at or a suitable justification explaining why this is not possible/appropriate for the study.

We aim to recruit 80 participants; 40 hypo- and 40 hyper- fatty acids tasters.

Power is estimated from a combination of the expected effects of both the sensory and energy manipulations. For the sensory effect, work has contrasted intake after equicaloric emulsion preloads varying in oil particle size and consequently perceived creaminess. A significant 12% reduction in meal size occurred using a within-participant design with 34 male participants in the small droplet-size (more creamy) preload (Lett et al., 2016).

In addition, we have based our calculation on the paper of Woodend 2001 where based on their results of the influence of a 836 kJ preload of safflower oil (of which the energy is similar to the 35g snack with 32% fat), a minimum sample size of 38 would be required to detect an intake change of 20%.

3.2

Will the research involve children or vulnerable adults (e.g. adults with mental health problems or neurological conditions)? No

If yes, how will you ensure these participants fully understand the study and the nature of their involvement in it and freely consent to participate?

(Please append letters and, if relevant, consent forms, for parents, guardians or carers). Please note: information letters must be supplied for all participants wherever possible, including children. Written consent should be obtained from children wherever possible in addition to that required from parents.

3.3

Will your research involve children under the age of 18 years? No

Will your research involve children under the age of 5 years? No

3.4

Will your research involve NHS patients, Clients of Social Services or will GP or NHS databases be used for recruitment purposes? No

Please note that if your research involves NHS patients or Clients of Social Services your application will have to be reviewed by the University Research Ethics Committee and by an NHS research ethics committee.

3.5

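### The only derived sample size (38 for a 20% intake change) rests on an energy gap that no Stage 3 contrast has, and the preload portion is given as 35, 40 and 50 g

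*Protocol*

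**What the plan says.** Section 3.1 (Sample Size) sets the total: "We aim to recruit 80 participants; 40 hypo- and 40 hyper- fatty acids tasters". It says that power combines sensory and energy effects, and cites one study for each.

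- Sensory: equicaloric emulsion preloads differing in droplet size. "A significant 12% reduction in meal size occurred using a within-participant design with 34 male participants". No sample size is derived from this.
- Energy: an "836 kJ preload of safflower oil (of which the energy is similar to the 35g snack with 32% fat"). From this, "a minimum sample size of 38 would be required to detect an intake change of 20" per cent.

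No alpha, power, SD, contrast or dropout is given.

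Section 2.2, Stage 3, Method item 1 describes a three-way cross-over of (i) full oil, "approximately 13g fat per 40 g snack portion"; (ii) the reduced-fat emulsion; and (iii) a "Negative control with the same % fat reduction as in sample (ii"), made by spraying less oil. Item 2 expects the low-fat snack "with matched sensory expected satiety will have a fat reduction of over 25 % but that this may reach a 60% reduction". The same item says of participants: "They will be given the test snack (pre-load study food, approximately 50 g"). Stage 2, Method item 1 shows a picture of a full portion of about 40 g. Stage 3, Method item 4 says that the power of the study concerns ad-libitum intake and not the biomarkers. The Stage 3 aim is that the emulsion snack, with a little added free fatty acid, should not lead to overeating.

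**The concern.** The 836 kJ in section 3.1 is matched to the energy of a whole snack, which would be the gap between eating the snack and eating nothing. Stage 3 has no such arm, so the energy basis of the 38 does not carry over to any comparison the trial makes. The sensory basis is closer to the emulsion question, but it is a precedent and not a calculation, and its effect (12%) is smaller than the 20% behind the 38.

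The emulsion contrasts carry the Stage 3 aim. If the stated size does not support them, a reader cannot tell what intake change the trial could detect there. The three portion weights add to this, because the energy difference between arms scales with the portion.

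**Working it through.** **1. Can the 38 be reproduced?** Not forward, because alpha, power and SD are missing. Working backwards with a paired t-test (noncentral t), two-sided 5%, n = 38 and a difference of 20%, the SD of the within-person difference is 42.9% of mean intake at 80% power or 37.0% at 90%. Normal approximation: 20 × √38 / (1.960 + 0.842) = 44.0%, or with 1.282 in place of 0.842, 38.0%. Other designs also give 38. A one-sided 5% test implies 49.6% or 42.1%; an unpaired comparison implies a between-person SD of 31.1% or 26.9% (38 per group), or 22.0% or 19.0% (19 per group). The figure is uncheckable, not shown to be wrong.

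**2. Energy difference between arms.** Inputs: 32% fat (section 3.1), 25-60% fat reduction (Stage 3, item 2), the three portions; assumed 37 kJ/g for fat and 15-17 kJ/g for the rest.

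| Portion | Fat (g) | Fat energy (kJ) | 25-60% of it (kJ) | Whole snack (kJ) | Whole snack / 836 |
|---|---|---|---|---|---|
| 35 g | 11.2 | 414 | 104-249 | 771-819 | 92-98% |
| 40 g | 12.8 | 474 | 118-284 | 882-936 | 105-112% |
| 50 g | 16.0 | 592 | 148-355 | 1,102-1,170 | 132-140% |

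Check with 13 g fat per 40 g: 13 × 37 = 481 kJ, and 25-60% of it is 120-289 kJ.

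The fourth column applies to full oil vs emulsion and equally to full oil vs negative control, since both reduced-fat snacks have the same percentage reduction. It is 12-42% of 836 kJ (104/836 to 355/836). Emulsion vs negative control has about no gap from fat.

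**3. Does the meaning of the 20% matter?** Section 3.1 does not say whether 20% is the effect of 836 kJ or a chosen detectable change. On the first reading, no contrast has that energy gap. On the second, 20% exceeds the 12% that is the only effect cited for a comparison with energy held equal, and no effect is cited for a gap of 104-355 kJ. Neither reading makes 38 a basis for the emulsion contrasts.

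**4. Power for 12%.** Paired t-test, two-sided 5%. Two SDs come from step 1. The others come from the cited significant 12% in 34 people: SD = 12 × √34 / t, with 33 df and t = 2.035, 2.445 or 2.733 for an assumed p of 0.05, 0.02 or 0.01.

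| Source of SD | SD (% of intake) | Power, n = 40 | Power, n = 80 |
|---|---|---|---|
| 38 for 20%, 80% power | 42.9 | 41% | 70% |
| 38 for 20%, 90% power | 37.0 | 52% | 82% |
| 12% in 34, p = 0.05 (largest SD) | 34.4 | 58% | 87% |
| 12% in 34, p = 0.02 | 28.6 | 73% | 96% |
| 12% in 34, p = 0.01 | 25.6 | 82% | 98.5% |

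The two cited results do not share one SD on the paired reading: with 42.9% or 37.0%, 12% in 34 people gives t = 1.63 or 1.89, p = 0.11 or 0.07, which is not significant.

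**5. Detectable change at the power behind the 38.** If the 38 was a paired calculation: 19.5% at n = 40 and 13.6% at n = 80, the same for 80% and 90% power (simple scaling: 20 × √(38/40) = 19.5%; 20 × √(38/80) = 13.8%).

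**The case against.** The strongest reply is that no shortfall is proved. The 38 could come from an unpaired calculation. If so, and with an assumed within-person correlation of 0.5, power for 12% at n = 40 is 66-97%. A one-sided reading implies a larger SD at the same nominal power and lowers the two-sided figure. The lowest powers in the table use SDs that do not fit the cited 12% result. Nothing says that the intake contrasts are tested separately by taster group, and with 80 pooled and the SD taken from the 12% result, power is at least 87%. All of this stands. It limits what can be said about size, but it does not supply the missing link between the 38 and the emulsion contrasts.

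Four stronger readings are tempting, and the documents do not support them:

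- A reader might infer that full oil vs negative control is adequately covered by the 38. It has the same fat gap as full oil vs emulsion, so the energy argument applies to it equally.
- A reader might infer that 836 kJ matches the snack only at 35 g. That depends on the assumed energy of the non-fat part: at 15 kJ/g the 40 g snack is the closer match (105% against 92%). Only 50 g departs clearly.
- A reader might infer that a non-significant full oil vs emulsion difference will be taken as proof that overeating is avoided. The protocol states an aim; it nowhere states that decision rule.
- A reader might infer that emulsion vs negative control is purely sensory with 12% as its planned effect. The added free fatty acid may act beyond the mouth, and 12% is cited as a precedent, not set as the target. It is still the only effect offered for that kind of comparison.

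**Conclusion.** The point holds as a fault in the stated basis of the sample size, not as a demonstrated lack of power. The 836 kJ behind the 38 is not the energy difference between any two Stage 3 arms: the gap is about 104-355 kJ against full oil (assuming 37 kJ/g and the stated 25-60% reduction) and about none from fat between emulsion and negative control. The 38 for 20% therefore does not support the claim that the study is powered on intake for the emulsion contrasts. Under a paired two-sided 5% test, power for the cited 12% is about 41-82% at n = 40 and about 70% to just over 98% at n = 80; other readings of the 38 widen this. It would be too strong to conclude that the trial is underpowered or that 38 is miscalculated.

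The portion conflict needs no assumption: 35 g in section 3.1, about 40 g in Stages 2 and 3, about 50 g in Stage 3, with 40 and 50 g both within the Stage 3 method. Assuming 15-17 kJ/g for the non-fat part, the 50 g serving carries 32-40% more energy than 836 kJ.

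**What to change.** Reword section 3.1, without enlarging the trial:

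1. Name the intake contrast that the size applies to, and say whether the n is 40 per taster group or 80 pooled.
2. Stop resting the emulsion contrasts on the 836 kJ and 20% figure.
3. Restate the detectable change for the planned n (about 19.5% at 40 and 13.6% at 80 at the original power, if the 38 was a paired calculation) and the power for the cited 12%, with the alpha, power and SD used.
4. Reconcile the 35, 40 and 50 g passages across section 3.1 and Stages 2 and 3, and state the resulting energy difference between arms.

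The cost is protocol wording and retrieving the inputs behind the 38. No participants or procedures are added. The downside is that the stated sensitivity becomes less favourable.
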